## Study Protocol

### **2.A.3. Research Design and Methods.**

**2.A.3.a. Approach.** To test the feasibility of a group-based education and skill-building rehabilitation (ESBR) intervention in improving dementia caregiver and care recipient outcomes, our proposed trial will consist of 40 family caregivers coping with all-cause dementia who will be randomized to ESBR. Twenty participants will be randomized to receive mobile media ESBR (ESBR-m), and 20 participants will be randomized to receive usual care plus supplemental educational materials on dementia (UC).

The results of this project will determine the efficacy of a low-cost, pragmatic intervention for caregivers of Veterans with all-cause dementia and will be used to build upon prior findings indicating the efficacy of resource-intensive methods to rehabilitate caregivers of Veterans with all-cause dementia.

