#### **2.A.3.b. Participants**

Inclusion criteria - Participants must:	Exclusion criteria - Participants will be excluded for:

• be adults (age <math>\geq 18</math>)

• report distress associated with being the primary caregiver for a family member with dementia

• reporting at least 2 of the following 6 items at baseline assessment: felt overwhelmed, felt like they often needed to cry, were angry or frustrated, felt they were cut off from family or friends, reported moderate to high levels of general stress, or felt their health had declined

• provide at least 7 hours of care (supervision or direct assistance) per week over the past 3 months (other sources of caregiving for the Veteran with dementia can also be utilized; e.g., respite, home health aide, other family members)

• cohabitate with a Veteran diagnosed with dementia

• be proficient in spoken and written English

• be capable of providing informed consent

	

• current or lifetime history of any psychiatric disorder with psychotic features

• prominent suicidal or homicidal ideation

• having met DSM-IV criteria for drug or alcohol abuse or dependence (except nicotine) within the past six months

• presence of alcohol intoxication (by breathalyzer) or alcohol withdrawal (by exam) during study recruitment or participation

• diagnosis of probable or possible dementia

• a Telephone Cognitive Screen score of <math>< 20</math>

• participation in another caregiver intervention study within the past year

• lack of access to telephone and internet services in the home

• illness that would prevent study participation

• planned transfer of care receiver to another caregiver or nursing home within 6 months

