experience. For example, we will send out thank you cards to all participants and will make follow-up telephone calls to express gratitude for participation. We will follow procedures that we have successfully used in our previous research.

**2.A.3.e. Screening Procedures.** Participant screening for eligibility and other data collection will mainly occur during telephone interviews. Should caregivers prefer, face-to-face (in-person) screening/assessment will also be offered. An interview will be conducted with caregivers to determine study eligibility. During this interview, study staff will explain the study, its requirements, and answer any questions the potential participant may have. Upon the potential participant's willingness to be screened, study staff will ensure all inclusion criteria are met and screen the potential participant for all exclusionary criteria. The results of all screening assessments will be reviewed by the PI in consultation with Co-I's. After consensus determination of study eligibility, the Study Coordinator will contact the participant to schedule a Baseline assessment (if eligible), or provide appropriate referral (e.g., VA Caregiver Support Program) and explanation (if not deemed eligible). Both "screen failures" and eligible participants who drop out prior to receiving any intervention will be replaced.

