### **2.A.3.f. Procedures Involving Eligible Participants**

#### **2.A.3.f.1. Enrollment, Randomization, and Baseline Assessment**

Enrollment and Randomization. Once participants are deemed eligible, they will be invited by the Study Coordinator to participate in the study, if willing and able to provide informed consent. At this point, the Data Manager will randomize the participant to one of two arms: ESBR-m or UC. For randomization, a modification of the Efron procedure (Efron, 1971) developed by [name] (Kraemer, 1981) will be implemented to assure the two groups are comparable at baseline in terms of dementia subtype. Participants who drop out after receiving any intervention will not be replaced, but their data will be used in mixed-effects analyses.

Baseline Assessment. Trained study staff, blind to the participants' ESBR-m/UC assignment, will administer a baseline assessment including clinicodemographics and measures of caregiver burden, depression, and perceived stress, in addition to care recipient functional status (see Section 2.A.3.g. for a description of outcome measures). Assessment will mainly occur over the telephone to reduce study participation burden. Packets with assessment aids will be sent to the caregiver prior to each assessment. Should caregivers prefer, in-person assessments will also be offered.

Mental Health referrals to Stanford Outpatient Psychiatry Clinics will be offered to all participants who score 16+ on the CES-D, in addition to participants who endorse symptoms of significant clinical concern, as determined by study staff. All participants are also provided information on accessing the VA Caregiver Support Program and the Veterans Crisis Line.

**2.A.3.f.2. Mobile Media Education and Skill-Building Rehabilitation Intervention (ESBR-m).** Our ESBR-m intervention consists of four, 90-minute group ( $\leq 5$  participants) sessions. **These four sessions are supplemented with a booster session one month following the last intervention session.**

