Title: Mobile Tablet Education to Advance Caregiver Health

NCT #: NCT03417219

March 3, 2014

**2.A.3.g. Study Measures.** *Zarit Burden Interview (ZBI)* [1]. Several versions of the ZBI have been used successfully as outcome measures in interventions for dementia caregivers [2, 3]. *Center for Epidemiological Studies-Depression (CES-D)* [4]. The CES-D is frequently used to assess depression in dementia caregivers and has been shown to be sensitive to changes in caregiver depression post intervention [5]. *Perceived Stress Scale (PSS)* [6]. The PSS has been used successfully to measure perceived stress in dementia caregivers [7]. *Global Deterioration Scale (GDS)* [8]. The GDS is a semi-structured rating of functional status in degenerative dementia. It has been successfully used in prior studies of dementia caregiver intervention with adequate reliability [9]. *Telephone Cognitive Screen (T-CogS)* [10]. The T-CogS is a brief mental status examination designed to be administered over the telephone. Scores on the T-CogS strongly correlate with MMSE scores ( $r = 0.88$ ,  $p < 0.001$ ) [11]. An exclusion cutoff score of  $< 20$  on the T-CogS is chosen to match a MMSE cutoff of  $< 23$  [12]. *Caregiver Interview*. All caregivers will also be administered a structured interview to ascertain information on levels of socialization and pleasurable activity participation.

**2.A.3.h. Data Management.** Integrity of data collection, scoring, and entry/verification will be overseen by the MIRECC Data Analyst/Database Manager and the PI.

**2.A.3.i. Statistical Analyses.** While the proposed project is designed to assess study feasibility, to test the hypotheses outlined in the Specific Aims (Section 2) we will use mixed-effects modeling to fully utilize outcome data measured over time (baseline and follow-up assessments) and to better handle missing outcome information in line with the intention to treat principle. [name] will serve as a statistical consultant, given her expertise in clinical trial and mixed modeling methodologies.

1. Zarit, S., *The hidden victims of Alzheimer's disease: Families under stress*. 1985: NYU Press.

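### Baseline appears to follow randomisation while an inclusion criterion is scored at it, and the SAP leaves open how baseline enters the two-visit model

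*SAP*

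**What the plan says.** **Order of steps.** Protocol 2.A.3.b lists as an inclusion criterion "reporting at least 2 of the following 6 items at baseline assessment". Section 2.A.3.e has staff check all inclusion criteria at a screening interview, and then: "After consensus determination of study eligibility, the Study Coordinator will contact the participant to schedule a Baseline assessment (if eligible"). Section 2.A.3.f.1 takes a participant who is eligible, invited and willing to consent, and continues: "At this point, the Data Manager will randomize the participant to one of two arms". The next paragraph of that section describes the baseline assessment, given by staff blind to assignment. Nothing says when the caregiver learns the arm.

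**Model.** SAP 2.A.3.i applies mixed-effects models to "outcome data measured over time (baseline and follow-up assessments"), to handle missing outcomes in line with intention to treat. It states no fixed effects, contrast, constraint on baseline means or covariates.

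**Allocation.** The modified Efron procedure in 2.A.3.f.1 "will be implemented to assure the two groups are comparable at baseline in terms of dementia subtype". The SAP has no subtype term.

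**The concern.** Two things are linked.

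First, 2.A.3.e and 2.A.3.f.1 together place baseline after randomisation, while 2.A.3.b makes eligibility depend on items collected at baseline. Taken literally, a caregiver could be randomised and then found ineligible. Because 2.A.3.e replaces screen failures, such a person might be dropped and replaced after allocation. Separately, baseline reports of burden, depression and stress come from a caregiver who may already know whether they will get the groups and tablet or usual care.

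Second, the model sentence fits both a common-baseline-mean model and one with free baseline means and an arm-by-time contrast. With two visits and complete data the latter is the change-score comparison, usually the less precise of the two. With 40 caregivers the main statistical product is an effect estimate with a wide interval, and baseline handling is a nearly free way to narrow it. The points belong together because a common baseline mean is justified only if baseline is unaffected by assignment.

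**Working it through.** **Sequence, side by side**

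| Section | What it implies |
|---|---|
| 2.A.3.b | baseline assessment, then eligibility |
| 2.A.3.e | eligibility, then baseline scheduled |
| 2.A.3.f.1 | eligibility and consent, then randomisation; baseline described next, by staff blind to assignment |

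Sections 2.A.3.e and 2.A.3.f.1 are compatible. Only 2.A.3.b is out of line with them.

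**Bias if knowing the arm shifts reported baseline.** Suppose one arm's baseline moves by d, and a fraction f of the shift remains at follow-up. With equal SDs and baseline-to-follow-up correlation rho:

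- change score: bias = d(f − 1)
- ANCOVA or common baseline mean: bias = d(f − rho)

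For an assumed d = 0.2 SD:

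| | Change score | Baseline-adjusted, rho 0.5 | Baseline-adjusted, rho 0.7 |
|---|---|---|---|
| Shift gone (f = 0) | −0.20 | −0.10 | −0.14 |
| Shift persists (f = 1) | 0 | 0.10 | 0.06 |

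Neither fit is safe in both cases.

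**Precision.** The plan gives no power, SD or variance to reproduce. From the documents: 20 per arm (Protocol 2.A.3.a) and two visits. Assumed: rho, follow-up SD k times baseline SD (baseline SD = 1), complete data and independent participants. With n = 20 per arm:

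- Free baseline means, arm-by-time contrast: V_free = (2/n)[k²(1 − rho²) + (1 − rho·k)²]. At k = 1 this is 4(1 − rho)/n.
- Baseline-adjusted: V_adj = (2/n)·k²(1 − rho²)·[1 + 1/(2n − 4)]. The bracket, 37/36, is the cost of estimating the slope.
- At k = 1 the ratio is (1 + rho)/2 × 37/36.

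| rho (k = 1) | V_free | V_adj | Net cut |
|---|---|---|---|
| 0.3 | 0.140 | 0.0935 | 33% |
| 0.5 | 0.100 | 0.0771 | 22.9% |
| 0.7 | 0.060 | 0.0524 | 12.6% |
| 0.9 | 0.020 | 0.0195 | 2.4% |

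Break-even is at rho = 2 × 36/37 − 1 = 0.946. Simulation (60,000 trials per setting) gave 22.9% at rho 0.5 and 12.9% at 0.7. In four simulated data sets the common-baseline-mean model, by ML and by REML, matched ANCOVA to four decimals.

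The 95% half-widths from these closed forms, with t = 2.024 (38 df) and 2.026 (37 df), are:

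- rho 0.5: 2.024√0.100 = 0.64 SD, falling to 2.026√0.0771 = 0.56 SD
- rho 0.7: 0.50 SD, falling to 0.46 SD

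**Sensitivity of the net cut (rho 0.5, rho 0.7)**

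- k = 0.8: 41%, 36%.
- k = 1.25: 8%, −1%. For the last, V_free = 0.1(0.7969 + 0.0156) = 0.0813 and V_adj = 0.0797 × 37/36 = 0.0819.
- 20% missing follow-up (simulated): 19%, 10%.
- ICC 0.05 in ESBR-m groups of five (simulated): 21%, 11%.

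**Subtype term.** With a biased coin of 2/3, rho 0.5 and a non-prognostic subtype (6,000 trials), adding the term multiplies variance by 1.007, 1.028, 1.039 and 1.042 for two to five assumed categories.

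**The case against.** **Order.** A reader might infer that all three protocol sections contradict one another. They do not: 2.A.3.e and 2.A.3.f.1 agree, and 2.A.3.e already has staff confirm every inclusion criterion at screening. The phrase in 2.A.3.b may be loose wording for that interview. This stands as a limit on the conflict, but the sequence on which the two sections agree is the one that puts baseline after allocation.

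**Bias.** No passage says caregivers know their arm at baseline, and the 0.2 SD shift is invented for scale. Nor are all baseline measures caregiver self-report: SAP 2.A.3.g describes the Global Deterioration Scale as a semi-structured rating of functional status. A shift that persists leaves the change score unbiased, so it is wrong to say every fit is equally exposed. All of this is right. The risk is unaddressed, not demonstrated.

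**Model.** One might infer that the SAP has chosen the weaker fit. It has not; its sentence equally admits a common baseline mean. One might also infer an inflated type I error, since keeping the smaller p-value of the two fits gives about 7% in simulation. That presumes conduct the documents do not describe, and they state no alpha. The Specific Aims that the SAP cites are not in the public text and may narrow the hypotheses. The precision gain depends on assumptions and may differ by scale.

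**Subtype.** Leaving it out is not an error. It does not inflate type I error, and its benefit cannot be sized from the documents.

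**Purpose.** The SAP says "While the proposed project is designed to assess study feasibility". That lowers the stakes, but the same sentence goes on to hypothesis tests, and Protocol 2.A.3.a speaks of determining efficacy.

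**Conclusion.** The point holds in two parts. The protocol should be reconciled so that eligibility and baseline are settled before allocation: as written, an inclusion item is scored at an assessment that appears to follow randomisation, with only the assessors blinded. With that order secured, naming a common-baseline or baseline-adjusted contrast is a near-free gain over the free-baseline fit that the SAP allows: about 23% of variance at rho 0.5 and 13% at rho 0.7. This assumes equal SDs, complete data, independent participants and 20 per arm. The gain is near nil at rho 0.9, or at rho 0.7 with follow-up SD 1.25 times baseline SD. None of these correlations or SDs is in the documents. Severity is low to moderate: the interval stays wide under either fit, and no decision in the documents is shown to change.

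**What to change.** 1. In Protocol 2.A.3.f.1, state that all eligibility items and the baseline assessment are completed before randomisation, or at least before the caregiver learns the assignment. Reconcile 2.A.3.b with 2.A.3.e and 2.A.3.f.1.
2. With that order in place, specify in SAP 2.A.3.i either a two-visit mixed model (common baseline mean, time, arm-by-follow-up contrast, unstructured 2×2 covariance, small-sample degrees of freedom) or ANCOVA of follow-up on arm and baseline score. If the order cannot be assured, do not make either fit primary without saying that baseline may be affected by assignment. The change score is then safe only if any shift persists.
3. Optionally, add the subtype categories used in allocation, with a rule for pooling sparse categories fixed before outcomes are seen.

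The cost is wording, plus holding randomisation until the baseline call is done; no new data are needed. The subtype term costs about 1% to 4% of variance if subtype is not prognostic. Clustering by ESBR-m session group is a separate matter that these changes do not resolve.
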